6 METHODS FOR THE STATISTICAL ANALYSIS

The analysis methods to be used to achieve the study objectives and draw up the descriptive content for the variables are detailed below.

❖ UNIVARIATE ANALYSIS

Quantitative variables will be described with centralization and scattering measures (mean, SD (standard deviation), median, minimum, maximum, Q1 (first quartile), Q3 (third quartile and N).

Qualitative variables will be described by absolute and relative frequencies. Two columns of percentages will be presented: Total Percentage (Total %) and Valid Percentage (Valid %):

- Total Percentage (%): Percentage of the sum of valid responses plus missing values, i.e. of the total of the sample under study.
- Valid percentage (Valid %): Percentage of total valid responses, i.e. with data on the variable.

In subgroup analyses, only the valid % with respect to the total for each group will be presented.

For questions with more than one answer option, **multiple response** tables will be shown. Two percentage column will be shown in these tables:

- Total percentage (%) Percentage of the sum of valid responses plus missing values, i.e. of the total of the sample under study. Since it is multiple choice, the sum of percentages does not have to be 100 (the percentage may be exceeded).
- Valid percentage (%) Percentage of the number of patients with at least one given answer from among the possible answers. Since it is multiple choice, the sum of percentages does not have to be 100 (the percentage may be exceeded).

Missing data will not be attributed and will be left as lost data.

Statistical analysis of variables collected in the study will be performed using the SPSS statistical program.

NOTE 1: Due to the small number of patients available in the study, no comparisons will be made and the associated p-value will not be shown. Only descriptive analyses will be presented.

NOTE 2: The texts collected in open fields will not be grouped, other than to standardize format and spelling. If desired, any grouping must be performed by the sponsor and as an additional table to the description of what is included in the database.

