6.1 Visit reassignment

6.1.1 Numerical variables at follow-up (neurological and scales)

In the section on variables in follow-up, there are visit dates and no months assigned to those visits. To avoid time variability and ensure consistency of the data, for each quantitative follow-up variable, the following procedure will be calculated. All values will be assigned, as of the follow-up date, weighing the assignments based on the recorded follow-ups.

1. Months between visits:

Firstly, the date difference between the first follow-up and the start time will be calculated for the variable in question. Values will be assigned to those visits that are close to this difference or lower, i.e. if the difference is 25 months, visits up to Month 24 will be allocated (see note 3 below).

2. Monthly unit change (exchange rate):

$$\frac{(\text{value at follow-up visit} - \text{value at start of treatment visit})}{\text{months between visits}}$$

3. Increment for each visit:

Monthly unit change x 6

Monthly unit change x 12

Monthly unit change x 18

Monthly unit change x 24

Monthly unit change x 36

4. Value assigned at each visit:

Baseline value + Increment for each visit

NOTE 3:

- In case only one follow-up is available and the total follow-ups cannot be assigned, the “last value carried forward” (LVCF) method will be used, so the last value obtained will be carried over to the end.
- If more than one follow-up is available and the difference between their dates is:
 - Less than 5 months, the value will not be allocated, as the two visits would be very close to each other.
 - Greater than 5 months and less than 10 months, the value of that follow-up will be assigned to the next follow-up pending assignment. That is, if the assignment of the first follow-up

reaches month 24, the assignment of month 36 would be considered as the value recorded in the second follow-up.

– Otherwise, if the difference is greater than 10 months, the values will be assigned with the algorithm from step 1 taking the previous follow-up as baseline.

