10.3 Neurological variables in patients

10.3.1 NIS (Neuropathy Impairment Score)

See Section 6.1.1 for numerical reassignment of visits.

Descriptive statistics (Mean, SD, Median, Minimum, Maximum, Q1, Q3 and N) of the following quantitative variables will be displayed:

- NIS result (total score ranges from 0 to 244), assigned value for each visit.
- The variable change in NIS between each of the months from start of treatment will be calculated*, which will be the variable corresponding to the increase for each visit in reassignment:
 - Month 6 - start of treatment.
 - Month 12 - start of treatment.
 - Month 18 - start of treatment.
 - Month 24 - start of treatment.
 - Month 36 - start of treatment.
- To the extent possible, paired parametric (t-test) or non-parametric (Wilcoxon) statistical tests will be performed, depending on the sample distribution, to study whether there are differences in the unit change rate for pre- and post-treatment NIS (total and subgroups).

In addition, a listing will be presented per patient for NIS: In the 12 months prior to enrollment in studies B3461028 and/or LTE B3461045 or start of treatment* and follow-up (from month 6 to month 36).

*Note: Start of treatment would refer to the clinical parameters available in the medical history in the 12 months before inclusion in studies B3461028 and/or LTE B3461045, or inclusion in studies B3461028 and/or LTE B3461045 (start of treatment with Tafamidis 61 mg). For each patient, only the most recent value will be collected.

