10.3.2 NIS-LL (Neuropathy Impairment Score Lower-Limbs)

See Section 6.1.1 for numerical reassignment of visits.

Descriptive statistics (Mean, SD, Median, Minimum, Maximum, Q1, Q3 and N) of the following quantitative variables will be displayed:

- NIS-LL result (total score ranges from 0 to 88), assigned value for each visit.
- Increase for each visit (monthly unit change x month).
- To the extent possible, parametric (paired t-test) or non-parametric (Wilcoxon) statistical tests will be performed, depending on the sample distribution, to study whether there are differences in the unit change rate for pre- and post-treatment NIS-LL (total and subgroups).

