12.2 Secondary objectives

12.2.1 Secondary objective 1

“To determine the efficacy of Tafamidis 61 mg in ATTRv patients with neurologic involvement included in studies B3461045 and/or LTE (B3461045) in Spain using additional non-cardiac variables at 6, 12, 18, 24 and 36 months after the start of treatment”

NOTE: ATTRv patients are considered to be those who have indicated “Mutation” in the genotype (“Data related to the disease at diagnosis”).

Results will be presented in each month (6, 12, 18, 24 and 36) (see section 6.1 visit reassignment).

Secondary objective 1 [sic: 2] variables:

- NIS at 6, 18, 24 and 36 months (see section 10.3.1)
- NIS-LL (section 10.3.2), Norfolk QoL-DN (section 10.5.1), COMPASS-31 (section 10.5.3) and FAP-RODs (section 10.5.2), FAP (section 10.3.3)
- % of patients whose stage does not progress in the PND score (section 10.3.4). N and % of patients whose stage does not progress in the PND will also be obtained, referring to patients who do not change to higher stages compared to the start of treatment.
- % of treatment responders. N and % of responder patients will be calculated for this objective, with responder being defined as:
 - **NIS:** Results will be presented in each month, defining responder as:
 - change at 6 months from baseline <2p in NIS, patients who have achieved less than 2 points in the NIS.
 - change at 12 months from baseline <4p in NIS, patients who have achieved less than 4 points in the NIS.
 - change at 18 months from baseline <6p in NIS, patients who have achieved less than 6 points in the NIS.
 - change at 24 months from baseline <8p in NIS, patients who have achieved less than 8 points in the NIS.
 - change at 36 months from baseline <12p in NIS and, patients who have achieved less than 12 points in the NIS.

Patients who do not meet the previous condition in each month will be considered non-responders. If complete data is not available, the value will be left as missing.

- **NIS-LL:** Results will be presented in each month, defining responder as:
 - change at 6 months from baseline <1p in NIS-LL, patients who have achieved less than 1 point in the NIS-LL at Month 6.
 - change at 12 months from baseline <2p in NIS-LL, patients who have achieved less 2 points in the NIS-LL at Month 12.
 - change at 18 months from baseline <3p in NIS-LL, patients who have achieved less than 3 points in the NIS-LL at Month 18.

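### With a single follow-up before Month 36, the carry-forward rule freezes a NIS or NIS-LL value while the responder cut-off keeps rising, so a non-responder can become a responder without new data

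*SAP*

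**What the plan says.** SAP 6.1.1 turns irregular visits into values at Months 6, 12, 18, 24 and 36, scale by scale. Step 1 fills the months close to or below the time of the first follow-up; in its example, a 25-month gap fills months up to 24. Steps 2 to 4 compute a monthly rate, multiply it by the month (the list ends at "Monthly unit change x 36") and add the result to baseline. NOTE 3 covers the remaining months: "In case only one follow-up is available and the total follow-ups cannot be assigned", the LVCF "method will be used, so the last value obtained will be carried over to the end".

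SAP 12.2.1 defines responders by cut-offs that grow with time. The Month-12 NIS rule reads "change at 12 months from baseline <4p in NIS, patients who have achieved less than 4 points in the NIS". The NIS series is 2, 4, 6, 8, 12 points at Months 6, 12, 18, 24, 36; the NIS-LL series is 1, 2, 3, 4, 6. At Month 36 the NIS-LL rule also requires NIS change below 12. SAP 12.2.2 (ATTRwt) uses only the combined NIS and NIS-LL rule.

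On missing data, SAP 6 says: "Missing data will not be attributed and will be left as lost data". SAP 12.1 and 12.2.1 leave responder status missing when data are incomplete; 12.2.2 has no such sentence. SAP 10.3.1 describes the NIS change as the variable "which will be the variable corresponding to the increase for each visit in reassignment", and 10.3.2 lists "Increase for each visit (monthly unit change x month").

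**The concern.** The cut-offs amount to a limit on the rate of worsening: 4 NIS points or 2 NIS-LL points per year. Where a month is filled by interpolation, the assigned change is rate times month, so a patient has the same status at every filled month. Where a month is filled by carrying a value forward, the change stays put and the limit moves up. Lack of follow-up then counts as stabilisation.

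The percentage of responders is a named variable for secondary objectives 1 and 2. No comparator or formal comparison is planned for it, so the percentages themselves will be read as the evidence. The trigger is realistic: Protocol 9.9 lists scarce follow-up data as a limitation. The SAP also does not state whether NOTE 3 overrides the leave-missing sentences.

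**Working it through.** **Inputs.** Carry-forward rule and step 1: SAP 6.1.1. Cut-offs: SAP 12.2.1 and 12.2.2. Expected size, 10 ATTRv and 10 ATTRwt: SAP 4. Twelve-month follow-up check: SAP 5. The responder rules are read as change from baseline.

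**The plan's own example.** A single visit at 25 months fills Months 6, 12, 18 and 24, and Month 36 falls to NOTE 3. Suppose NIS has changed by +10. The rate is 10/25 = 0.4 per month. Month 24 is 0.4 × 24 = 9.6 against 8: non-responder. Month 36 is the carried 10 (or 9.6 if the last assigned value is carried) against 12: responder.

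**Slope of the cut-offs.** NIS: 2/6 = 4/12 = 6/18 = 8/24 = 12/36 = 1/3 per month. NIS-LL: 1/6 = 2/12 = 3/18 = 4/24 = 6/36 = 1/6 per month.

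**General form.** Let r be the monthly rate and m the scheduled month.
- Interpolated month: the change is r × m and the NIS cut-off is m/3, so the patient responds if r < 1/3, whatever m is.
- Carried month: the change is r × t, where t is the visit month (recorded value carried) or the last filled month (assigned value carried). The patient responds if r < m/(3t). Since m > t, this limit is looser than 1/3 and loosens further as m grows.

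For the NIS cut-offs, and for the NIS-LL cut-offs taken alone, a carried status can therefore move only from non-responder to responder. An exact grid confirms the direction (one visit at each of Months 6–35, change −10 to +40 in steps of 0.5; 3,030 combinations):

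| Scale | Value carried | Switches to responder | Switches back |
|---|---|---|---|
| NIS | recorded | 300 | 0 |
| NIS | last assigned | 478 | 0 |
| NIS-LL, points cut-off only | recorded | 145 | 0 |
| NIS-LL, points cut-off only | last assigned | 238 | 0 |

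These counts show direction, not how often it would happen.

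**Single visit at Month 12.**

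| Change at Month 12 | Rule | Month 12 | Month 18 | Month 24 | Month 36 |
|---|---|---|---|---|---|
| NIS +5 | NIS | No (5 vs 4) | Yes (5 vs 6) | Yes (5 vs 8) | Yes (5 vs 12) |
| NIS +5, NIS-LL +3 | combined | No (5 vs 4; 3 vs 2) | No (3 vs 3) | Yes (5 vs 8; 3 vs 4) | Yes (5 vs 12; 3 vs 6) |

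For NIS alone, a Month-12 change of 4 to below 6 becomes a response at Month 18, 6 to below 8 at Month 24, 8 to below 12 at Month 36, and 12 or more never.

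**Size of the loosening at Month 36.** With the recorded value carried, the effective NIS limit is 12 × 12/t points per year: 12 for a visit at Month 12, 8 at Month 18, 6 at Month 24, against 4 on interpolated months.

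**Reach to Month 12.** SAP 5 checks the patient's last follow-up date, not the date of the NIS. If the only NIS is at Month 8 with +3.5, Month 6 is 3.5 × 6/8 = 2.625 against 2 (non-responder), while Month 12 carries 3.5 against 4 (responder).

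**Effect on a rate.** One switch in 10 patients is 1/10 = 10 percentage points. Compared with leaving months missing, the direction depends on who is carried. Assumed example: 7 patients observed at Month 36 with 5 responders, plus 3 with only a Month-12 visit. If the 3 are at +5, carry-forward gives 8/10 = 80% against 5/7 = 71%. If they are at +14, it gives 5/10 = 50% against 71%.

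**The case against.** The best defence is that NOTE 3 is a specific rule for follow-up scales and so overrides the general sentence in SAP 6, and that complete data in 12.2.1 means data after visit reassignment, since that section points to 6.1. This is a fair reading, although the SAP does not state it. It weakens the charge of contradiction but does not remove the switch: applying NOTE 3 is what produces it.

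A reader might infer that SAP 10.3 and 10.5 set up a firm third rule that extrapolates the rate, so that NIS +5 at Month 12 becomes +15 at Month 36. The documents do not support that. Step 1 stops allocation near the visit, and 10.3 and 10.5 refer back to 6.1.1. Only the unqualified rate-times-month wording suggests it, and that is a drafting point.

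A reader might also infer that no responder can ever lose that status. That fails for the Month-36 NIS-LL rule as written. With NIS +13 and NIS-LL +1 at a single Month-12 visit, the patient is an NIS-LL responder at Months 12, 18 and 24 and a non-responder at Month 36, because NIS is not below 12.

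It is also fair that these are descriptive results in about 20 patients and that some carried scores could be spotted: "In addition, a listing will be presented per patient for NIS". But no flag is required, the reported N would count carried values, and no such listing is required for NIS-LL.

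**Conclusion.** The point holds and should be fixed. For NIS, and for NIS-LL judged on its own points cut-off, a carried status can change only towards response, and does so without new data. The combined rule, the only one used for ATTRwt, shows the same switch in the worked case. The tension with the leave-missing sentences in SAP 6, 12.1 and 12.2.1 is real but could be settled by a stated precedence; the switch would remain.

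The reach is limited. It needs a single follow-up for that scale and a change inside the ranges shown. It concerns mainly the Month 18–36 responder rates of secondary objectives 1 and 2, at about 10 percentage points per patient switched. A reader might infer that the primary Month-12 result is compromised or that reported rates must be inflated. Neither follows. Month 12 is touched only if the sole NIS is too early for step 1 to fill that month. Against leaving months missing, the rate can move either way, because carried patients who stay non-responders also enter the denominator. Carry-forward does overstate the rates if patients go on worsening at their observed rate, which is an assumption. The documents do not give the number of patients affected.

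**What to change.** - Replace the carry-forward bullet in SAP 6.1.1 NOTE 3 with: *If only one follow-up is available, values are assigned up to the last month that step 1 covers; later months are left missing.*
- Give the closeness condition in step 1 a numerical window, so that it is clear which month a visit at, say, Month 11 or 35 fills.
- Apply the rule to the score, its change and responder status, and limit the rate-times-month wording in 10.3 and 10.5 to the months that step 1 covers.
- Repeat the missing-data sentence of 12.2.1 in 12.2.2.
- Show the number of patients with an assigned value beside each monthly responder percentage.

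The cost is a few lines of SAP text and no new data. N will be smaller at Months 18–36, and a Month-12 value may be lost for a patient whose only NIS is earlier than the Month-12 window. The available-case rate may be biased in either direction if length of follow-up is related to progression; state this as a limitation. Keeping carry-forward with flagged values and a sensitivity table would make the problem visible, but the main table would still contain the switch.

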12 ANALYSIS OF THE OBJECTIVES

12.1 Primary objective

“To determine the efficacy of Tafamidis free acid 61 mg in ATTRv patients with neurologic involvement included in studies B3461045 and/or LTE (B3461045) in Spain through changes in the 12-month NIS scale”

Primary variable: Neuropathy Impairment Score (NIS).

NOTE: ATTRv patients are considered to be those who have indicated “Mutation” in the genotype (Data related to the disease at diagnosis).

See resolution of this objective in 10.3.1 (month 12).

Additionally, the results will be presented for the percentage of patients responding to treatment of the change at month 12 with respect to the initial value. The N and % of patients responding to treatment will be calculated, defining responder as:

- change at 12 months compared to the initial data <4p in NIS, patients who have obtained less than 4 points in the NIS in month 12

Patients who do not meet the previous condition will be considered non-responders. If complete data is not available, the value will be left as missing.

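### A NIS recorded at or near Month 12 can be discarded because another follow-up was taken less than 5 months earlier, and the SAP does not settle what then stands at the primary time point

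*SAP*

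**What the plan says.** The primary objective (SAP 12.1) is the change in NIS at Month 12 in ATTRv patients. It is resolved through SAP 10.3.1, which takes its values from the visit reassignment in SAP 6.1.1. NIS-LL and the three scales in SAP 10.5 use the same reassignment.

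Under 6.1.1 the first follow-up fills the scheduled months at, below or near its own time: "Values will be assigned to those visits that are close to this difference or lower, i.e. if the difference is 25 months, visits up to", where the example ends at the 24-month visit. NOTE 3 then governs later follow-ups, starting from "If more than one follow-up is available and the difference between their dates is", with three branches:

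- Short gap: "Less than 5 months, the value will not be allocated, as the two visits would be very close to each other".
- Middle gap: "Greater than 5 months and less than 10 months, the value of that follow-up will be assigned to the next follow-up pending assignment".
- Long gap: "if the difference is greater than 10 months, the values will be assigned with the algorithm from step 1 taking the previous follow-up as baseline".

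Carry-forward is introduced with a condition: "In case only one follow-up is available and the total follow-ups cannot be assigned". Elsewhere, SAP 6 says "Missing data will not be attributed and will be left as lost data", and SAP 12.1 says of responder status "If complete data is not available, the value will be left as missing".

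**The concern.** The short-gap branch keeps or drops a real measurement by its nearness to another visit. How near it lies to the month it could fill plays no part. A NIS taken exactly at Month 12 can be set aside because the patient was also seen at Month 8, although the Month 8 value is the poorer guide to Month 12.

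The SAP also leaves open what happens next. It does not say whether a patient with one allocated and one unallocated follow-up counts as having only one follow-up for carry-forward. It does not say whether the next gap runs from the previous recorded visit or from the previous allocated one. Gaps of exactly 5 or exactly 10 months fall under no branch. Two programmers could follow the text and report different primary values for the same patient.

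The primary set is very small, and SAP 6 shows only valid percentages in subgroup tables. An ATTRv patient with an empty Month 12 therefore drops out of the responder denominator.

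**Working it through.** **Inputs.** Scheduled months 6, 12, 18, 24 and 36 and the rules above (SAP 6.1.1); responder cut-off at Month 12 of a change below 4 points (SAP 12.1); 10 ATTRv patients expected (SAP 4). The documents give no visit dates or NIS values, so those below are assumptions. The short-gap rule is read as dropping the later of the two visits.

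**The SAP's own examples.** A first follow-up at 25 months fills Months 6, 12, 18 and 24. A second at, say, 32 months (gap 7) puts its recorded value in Month 36. Both reproduce.

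**Example schedules.** Assume NIS = 20 + 0.5 × months, so the true Month 12 value is 20 + 0.5 × 12 = 26.0. A tolerance of 1 month is used for what counts as close.

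| Follow-ups (months) | Month 12 on the literal reading | Month 12 on the other reading |
|---|---|---|
| 12 alone; 6+12; 6+12+18+24; 12+15; 11+13 | 26.0 | 26.0 |
| 8+12 | empty | 24.0 (8-month value carried forward) |
| 9+13 | empty | 24.5 (9-month value carried forward) |
| 10+14 | empty | 25.0 (10-month value carried forward) |
| 8+12+20, gap from the recorded 12-month visit (20 − 12 = 8) | 30.0 (20-month value placed in Month 12) | same |
| 8+12+20, gap from the allocated 8-month visit (20 − 8 = 12) | 26.0 (interpolated from 8 to 20) | same |

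The literal reading denies carry-forward because two follow-ups exist. The other reading counts only the allocated follow-up. With 8+12+18, a gap measured from the recorded visit is 6 months and Month 12 receives the 18-month value, 29.0. Measured from the allocated visit the gap is exactly 10 months, which no branch covers; treated as a long gap, it gives 26.0. In every row from 8+12 down, the recorded NIS nearest Month 12 is not used. The 26.0 in the last row matches the truth only because a straight line was assumed.

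**How far the condition reaches.** Take two follow-ups, the second at month 11, 12 or 13 and the first at any earlier whole month: 10 + 11 + 12 = 33 pairs. The gap is 1 to 4 months in 3 × 4 = 12 pairs, so the second visit is dropped in 12 of 33. On the literal reading Month 12 is empty in 11, 9 or 6 of the 33 for a tolerance of 0, 1 or 2 months. It is empty in none if carry-forward is applied. Pairs ending at month 11 meet the 12-month follow-up check in SAP 5 only if a later visit without NIS exists. Without them there are 11 + 12 = 23 pairs, 8 dropped, and 7, 5 or 3 empty. These counts describe the rule and are not probabilities.

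**Effect on responder status.** Assume NIS 20 at baseline, 22 at 9 months and 25 at 13 months; the gap of 4 months drops the 13-month value.

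- Interpolating the two recorded visits: 22 + (25 − 22) × (12 − 9)/(13 − 9) = 24.25; change 4.25, non-responder.
- Nearest recorded value: 25; change 5, non-responder.
- SAP, literal reading: missing.
- SAP, carrying the 9-month value forward: 22; change 2, responder.

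**Effect on the primary table.** Each affected patient is 1/10 = 10% of the expected ATTRv set. If 6 of 10 were responders (assumed), losing one non-responder gives 6/9 = 67%, and turning that patient into a responder gives 7/10 = 70%, against 6/10 = 60%.

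**The case against.** The strongest reply is that the rule bites only in a particular pattern. The first follow-up is never subject to it, and the schedules in the first row of the table lose nothing. Protocol 9.9 warns of scarce follow-up data, and the SAP's own example has a first follow-up at 25 months, so dense visits may be uncommon. A later visit can also repair the gap. If it comes more than 10 months after the unallocated one, and that visit counts as the previous follow-up, it becomes the baseline for interpolation. All of this stands and limits the point to a conditional one.

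A reader might infer more than the documents support:

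- That NIS values near Month 12 are lost in general and the primary value is left empty. Loss needs another follow-up less than 5 months earlier that did not itself fill Month 12. Empty is only the literal reading with no later visit.
- That a patient with only a 9-month visit keeps a Month 12 value while a better-followed patient loses one. SAP 5 requires the last follow-up to be at least 12 months after treatment start, so the first patient would generally not be evaluable.
- That the affected patient is typical, or that the loss favours the drug. No visit dates are given. Bias towards the drug would need sites to see worsening patients more often, which is not shown.

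The objection does not rescue the rule where it applies. With follow-ups only at 8 and 12 or 9 and 13 months, both readings leave the best measurement unused.

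**Conclusion.** The concern holds in conditional form. SAP 6.1.1 states a rule that can discard the recorded NIS nearest the primary time point when an earlier follow-up, not close enough to fill Month 12, was taken in the preceding 5 months. Month 12 may then be missing, carried forward from the earlier visit, or filled from a later one, and the SAP does not say which. This is a stated rule that gives a worse value than the data allow, and not only a missing detail.

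The size is about 10% of the primary set per affected patient, given the SAP's estimate of 10 ATTRv patients. The number of such patients and the direction of any bias cannot be determined from the documents. The switch from non-responder to missing or responder rests on assumed NIS values chosen to show that the choice of reading can matter at the 4-point cut-off.

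**What to change.** In SAP 6.1.1, NOTE 3:

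- Delete the short-gap bullet.
- Where a scheduled month lies between two recorded visits (start of treatment counts as one), interpolate between those two visits whatever their spacing. The SAP already uses this method for gaps over 10 months. For bracketed months it replaces the middle-gap branch as well, and it covers gaps of exactly 5 and 10 months.
- Use a recorded value directly when it falls on the scheduled month.
- State in SAP 10.3.1 that the patient listing shows every recorded NIS with its date. The present text describes start of treatment and months 6 to 36 and does not say that unallocated values appear.

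No recorded value is then dropped because another visit is near it. In the 9- and 13-month illustration, Month 12 becomes 24.25, a change of 4.25. The cost is SAP wording and a few lines of programming; no new data are needed, because the reassignment already works from recorded visit dates.

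### SAP 6.1.1 NOTE 3 can put an NIS taken well after month 12 into the primary Month 12 slot, and after a restart the increment is no longer the change from start of treatment

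*SAP*

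**What the plan says.** SAP 6.1.1 works variable by variable. In step 1, "the date difference between the first follow-up and the start time will be calculated for the variable in question". The slots to be filled follow from that: "Values will be assigned to those visits that are close to this difference or lower". No number of months is given for how close is close. Each filled slot receives the start value plus the monthly change multiplied by 6, 12, 18, 24 or 36.

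NOTE 3 covers patients with more than one follow-up, by the gap between follow-ups:
- Under 5 months: the later value is not used.
- 5 to 10 months: "Greater than 5 months and less than 10 months, the value of that follow-up will be assigned to the next follow-up pending assignment". The SAP's illustration puts the second recorded value, unscaled, into Month 36 once Month 24 has been reached.
- Over 10 months: "the values will be assigned with the algorithm from step 1 taking the previous follow-up as baseline". The receiving slots are not named.

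SAP 10.3.1 labels the NIS change "Month 12 - start of treatment" and says of the same variable: "which will be the variable corresponding to the increase for each visit in reassignment". SAP 10.3.2 gives "Increase for each visit (monthly unit change x month" as its only measure of change, and the three parts of 10.5 do the same. SAP 12.1 takes the primary result in ATTRv patients from 10.3.1 at month 12 and adds a responder rate, defined as a change from the initial value of less than 4 points. On display, 10.3.1 says: "In addition, a listing will be presented per patient for NIS". The listing is organised by assigned month, and visit dates are not mentioned.

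**The concern.** The reassignment is meant to remove variability in visit timing. For one visit pattern it adds some. If the first NIS follow-up falls at 6 to under 12 months, it fills Month 6 and leaves Month 12 pending. A second NIS 5 to 10 months later then becomes the Month 12 value, whenever it was taken. With a longer gap the slot is not determined, and the increment counts only change since the previous follow-up.

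Both routes reach the primary variable. The first can give a mistimed Month 12 value from a rule followed exactly. The second leaves the primary change with two definitions that cannot both hold. Reporting descriptively, without p-values, gives no protection, because the problem lies in the estimate itself.

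**Working it through.** **The SAP's own illustration.** A first follow-up at 25 months fills Months 6, 12, 18 and 24. A second one 5 to 10 months later, at months 30 to 35, goes unscaled into Month 36. Coding the rule reproduces this, so the reading used below is the SAP's own.

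**Range of dates that can land in Month 12.** Month 12 is the next empty slot when the first follow-up is at 6 months or later but too early to fill Month 12 itself.
- Strict reading (only slots at or below the elapsed time): first visit at 6 to <12, plus a gap of 5 to 10, gives 11 to just under 22 months.
- Closeness tolerance of 1, 2 or 3 months: the first visit must be before month 11, 10 or 9, so the upper end is about 21, 20 or 19 months.

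**Effect on one patient, 5 to 10 month rule (assumed NIS path).** NIS 20 at start, 22 at month 8, 24 at month 17; gap 9 months.
- Assigned Month 12 change: 24 − 20 = 4, not below 4, so non-responder.
- Interpolated: 22 + (24 − 22) × (12 − 8)/(17 − 8) − 20 = 2.89, so responder.
- Effect at n = 10 (the SAP 4 estimate for ATTRv): responder rate 1/10 = 10 percentage points; mean change (4 − 2.89)/10 = 0.11 points.

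**Direction.** Under linear worsening the assigned change is the true Month 12 change multiplied by (month of second visit)/12. That factor is 11/12 = 0.92 at month 11, 17/12 = 1.42 at month 17 and 21/12 = 1.75 at month 21. With a second visit at month 17, any rate from 48/17 = 2.82 to just under 4 points per year is wrongly classed as non-response. A value taken before month 12 errs the other way: at 0.35 points per month the true change is 4.2, but a month 11.2 value gives 3.92 and a responder.

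**Restart after a gap over 10 months (assumed NIS path).** NIS 20 at start, 24 at month 8, 26 at month 20; gap 12 months; slope (26 − 24)/12 = 0.167 per month.

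| Reading of the Month 12 slot | Value | Value minus start | Increment |
|---|---|---|---|
| Interpolated at calendar month 12 (slope × 4) | 24.67 | 4.67 | 0.67 |
| Next pending slot (slope × 6) | 25.00 | 5.00 | 1.00 |
| Multiplier 12 from previous follow-up (slope × 12) | 26.00 | 6.00 | 2.00 |

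The increment is 4.0 points below the change from start on every reading, because it drops the 24 − 20 = 4 points that came before month 8. If the increment is reported, such a patient lowers the mean at n = 10 by 4.0/10 = 0.40 points. Under the 5 to 10 month rule no increment is computed at all, so the equation in 10.3.1 has nothing to refer to there.

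**The case against.** The strongest case accepts that the 5 to 10 month rule has no date window and disputes the rest.

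- *The affected group may be empty.* This stands as a limit on size. The documents give no visit dates, the SAP's illustration starts at 25 months (where Month 12 is interpolated properly), and protocol 9.9 warns that follow-up data are scarce. It does not excuse the rule, since NOTE 3 was written for patients with several follow-ups. Nor does eligibility help: the check in SAP 5 concerns the date of the last follow-up, and a patient seen at months 8 and 17 passes it.
- *The subtraction in 10.3.1 is the natural definition, and 12.1 also compares with the initial value.* This largely stands for the primary variable. A reader might infer that a restart turns non-responders into responders. The documents do not support that: with value minus start, the restart patient above is a non-responder on every reading. The understatement arises only if the increment is reported. However, 10.3.1 does equate the two, and 10.3.2 and 10.5 offer no subtraction to fall back on.
- *The error works against the drug.* Under steady worsening a late value overstates progression, so it would be wrong to infer that the 5 to 10 month rule flatters treatment.
- *Month 22 is an extreme.* Correct: it needs a first visit just short of 12 months that does not count as close to Month 12.
- *The listing may show dates.* The SAP does not mention them and does not exclude them. It is too strong to say that mistiming could not be seen.

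**Conclusion.** The point holds for a defined group: patients with more than one NIS follow-up, the first at 6 to under 12 months. With a second NIS 5 to 10 months later, the SAP followed as written can give a Month 12 value observed at about months 11 to 19-21, or just under 22 on the strict reading. One such patient can cross the 4-point cut-off and move the responder rate by 10 percentage points at n = 10. With a gap over 10 months, the slot is undefined and 10.3.1 contradicts itself; the mean change is understated if the increment is used.

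Confidence is high on the missing date window. The restart is an ambiguity and a contradiction to resolve, not a demonstrated error in the primary result. The NIS paths are assumptions, the number of patients affected is unknown, and no total group effect is claimed. Four patterns are not affected: a first follow-up at or after month 12; visits at 6 and 12 months; a first visit that fills no slot (Month 6 is then the next one pending); and a second visit less than 5 months after the first.

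**What to change.** 1. In SAP 6.1.1 NOTE 3, replace the 5 to 10 month rule and the over-10-month rule with: *The value at month m after start of treatment is the linear interpolation between the two dated visits of that variable, start of treatment included, that bracket m.* State openly whether visits less than 5 months apart are still dropped or serve as interpolation points.
2. In 10.3.1, 10.3.2 and 10.5, define change at month m as the assigned value at m minus the start-of-treatment value, and delete the equation with the increment. This agrees with 12.1.
3. Add actual visit dates to the per-patient NIS listing.

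For months up to the first follow-up, item 1 reproduces steps 1 to 4: with a first follow-up at 25 months the difference is 0 at Months 6, 12, 18 and 24. It differs where closeness lets the first visit fill a later slot. For example, NIS 20, 23 and 23 at start, month 11 and month 20 gives 3 × 12/11 = 3.27 under steps 1 to 4 and 3.0 by interpolation.

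The carry-forward rule for a single follow-up, and months after the last visit, are separate matters that this change does not settle. They include Month 36 in the SAP's own illustration.

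The cost is small: SAP wording and reprogramming, with dates and values already recorded. Protocol 9.7 sends major modifications of primary endpoint definitions or analyses to a protocol amendment, so the sponsor should record whether this counts as one.
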